### 6 Study Intervention

The health technology being assessed is giving birth in water: 'waterbirth'.

### 7 Study design and setting

A natural experiment using a cohort design with a qualitative component will answer the study objectives by using a combination of data captured retrospectively and prospectively in electronic NHS maternity and neonatal information systems. The qualitative component will explore factors associated with high and low rates of pool use; data will be gathered in online discussion groups, focus groups and one-to-one interviews with key stakeholders, including mothers/to be.

To answer all research objectives approximately 600,000 individual computerised maternity records held on secure NHS servers at around 30 NHS sites, covering the period January 2015 – November 2020 will be accessed. To provide necessary denominator data, and to be able to compare characteristics of pool users and non-pool users, a minimal data set will be extracted relating to women who did not use a pool in labour, whilst a more extensive dataset will be extracted for women who did use a pool in labour. An important clinical question is whether there is a differential effect of waterbirth on severe perineal trauma (OASIS) amongst nulliparous and parous women. To undertake this subgroup analysis will require a necessarily large sample (30,000). As data relating to perineal trauma and waterbirth are already captured, and to avoid unnecessarily prolongation of the study, this analysis will use a combination of retrospective and prospectively collected data, including births from 2015 to 2020.

The sample required for the neonatal primary outcome is smaller (16,200) and, as all essential data are not currently collected for one component of this composite outcome (antibiotic administration within 48 hours of birth on postnatal wards) additional data fields will to be added to maternity systems at participating NHS sites. Therefore, we will collect these data on births prospectively during the period June 2018 to November 2020.

Some neonatal outcomes of interest, including neonatal hypoxia, respiratory support or neonatal mortality, are already held by study sites or by the National Neonatal Research Database (NNRD). Where available and where the risk status, and pool usage of mothers can be determined, retrospective data will be utilised to increase the power of the analysis around secondary neonatal outcomes.

The NNRD holds individual patient level data on all babies admitted for National Health Service neonatal care in England, Scotland and Wales from 2014 to present. To obtain detailed treatment and outcome information on any baby who required admission to a neonatal unit, following their mother's pool use in labour, the identifiers of all babies born to women who used a pool during the period of prospective data collection will be extracted and matched to any records held by the NNRD.

The primary study aim is to compare maternal and neonatal outcomes for 'low risk' women who gave birth in water (Group 1) against 'low risk' women who left the water prior to birth for reasons other than clinical need (Group 2) Figure 1.

[figure not shown]

Figure 1 Study population groups

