### 4 Background

During labour and birth water immersion is facilitated by use of a conventional bath or more frequently a specialist birthpool. All birthpools offer sufficient depth of warm water for the woman to be immersed to above her breasts when sitting and sufficient space for ease of movement and change of position. Simple inflatable pools are available, but NHS maternity units frequently now have pools which are plumbed in, some of which are more complex with inbuilt lighting and heating. Women enter the warm water in established labour, leaving the pool either prior to birth due to clinical concerns or maternal choice, or remaining in the pool until after birth of the baby. Some mothers remain in the pool until after delivery of the placenta. For mothers the potential benefits of waterbirth are considered to be pain reduction, relaxation, reduced labour interventions and reduced perineal trauma whilst for babies, a gentle birth and transition to life. It is suggested that waterbirth may also improve longer term outcomes; mother infant bonding, increased breastfeeding and enhanced maternal postnatal mental health.

In 1992 the House of Commons Health Committee recommended that hospitals should provide women with the use of a birth pool for labour '*where this is practicable*. In the intervening years the popularity of the use of water immersion for labour and birth in the UK has increased and NICE guidance has recommended since 20071.4 that water immersion analgesia should be made available to all clinically appropriate women in labour. The Cochrane review of water immersion during labour provided evidence supportive of pool use but could not answer the question relating to the safety of waterbirth. The review included 12 trials (3243 women), eight related to just the first stage of labour: one to early versus late immersion in the first stage of labour; two to the first and second stages; and another to the second stage only. Results for the first stage of labour found a significant reduction in the epidural/spinal/paracervical analgesia/anaesthesia rate amongst women allocated to water immersion compared to no immersion (478/1254 versus 529/1245; risk ratio (RR) 0.90; 95% confidence interval (Cl) 0.82 to 0.99, six trials). There was also a reduction in duration of the first stage of labour (mean difference -32.4 minutes; 95% Cl -58.7 to -6.13). There was no evidence

TPL/003/2 v1.0

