### 5 Study objectives/endpoints and outcome measures

The primary study aim is to establish whether for 'low-risk' women who use a pool during labour, waterbirth, compared to leaving a pool prior to birth, is as safe for mothers and babies.

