### 5.4 Secondary Outcomes

Secondary outcomes of parental, clinical and financial importance have been identified. Data relating to maternal or neonatal readmission to hospital within seven days of birth is already reported by community midwives and captured in EuroKing® systems at the point of discharge from midwifery care. Data relating to some primary and secondary outcomes are not currently captured in EuroKing® maternity information systems and at site opening the EuroKing® E3 systems at sites will be amended to prospectively collect these data.

Maternal secondary outcomes: Maternal Intrapartum: Shoulder dystocia and required management, management of the third stage of labour, need and reason for obstetric involvement in woman's care including sepsis; mode of birth, maternal position at birth, treatment for haemorrhage, incidence and management of perineal and other genital trauma. Maternal Postnatal: duration of postnatal stay, breast feeding initiation and continuation, higher level care, and maternal readmission to hospital within seven days of birth.

Infant secondary outcomes: Snapped umbilical cord prior to clamping, skin to skin contact at birth, timing of cord clamping, resuscitation, Apgar scores, administration and duration of intravenous antibiotics. Incidence of: lumbar puncture, culture proven infection, brachial plexus injury; treatment for jaundice; readmission to hospital within seven days of birth; therapeutic hypothermia;

TPL/003/2 v1.0

Page **15** of **38** 

neonatal unit admission and duration; cause of neonatal death; respiratory support. Where available, and where the risk status and pool usage of mothers can be determined, retrospective data will be used in addition to prospective data, to describe the occurrence of these infant outcomes.

Additional data items with accompanying background development required to fully answer the research aims will be added to E3 systems at study sites, and will include:

- Maternal risk factors at pool entry
- Maternal risk factors developing during labour
- Time of entry into pool
- Time of last leaving pool
- Reason for leaving pool if prior to birth
- Partial birth in water (breech / shoulder dystocia)
- Birth position in pool
- Conversion from planned physiological to active third stage labour management.
- Delivery of placenta in or out of water
- Treatment for haemorrhage
- Reason for obstetric involvement in woman's care

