#### 9.6.5 Primary analysis

The primary analyses are based on a non-inferiority test of birth in water versus on land, comparing 1) the proportion of mothers that have OASIS, and 2)the proportion of babies with a composite outcome of 'adverse neonatal outcome or treatment'.

To test the primary hypothesis of non-inferiority between birth in water and on land, the two outcomes will be evaluated for non-inferiority using logistic regression models, in the first instance with no adjustment for covariates. Adjusting for potential confounders may result in a more precise treatment effect estimate. The potential confounders of both primary outcomes (listed in table 1) will be considered and the impact on bias through conditional associations when conditioning on these covariates will be assessed using directed acyclic graphs (DAGs). The main logistic model will incorporate these selected covariates through regression adjustment. Results will be reported as an (unadjusted) odds ratio (birth in water compared to on land), and a two-sided 90% confidence interval (CI) for the (unadjusted and adjusted) odds ratio will be calculated. Non-inferiority will be concluded if the upper limit of the 90% CI for the difference in neonatal outcome between the groups is less than 1.0% (OR<1.21). Similarly, for the mother's outcome, non-inferiority will be concluded if the upper limit of the 90% CI for the difference in the proportion of OASIS between the groups is less than 1.0% (OR<1.23) in nulliparous 'low-risk' women and less than 0.6% (OR<1.38) in parous 'low-risk' women. The data will then be combined to assess the effects averaged across both strata.

If non-inferiority is shown, then a superiority analysis will be conducted as a secondary analysis of the primary outcomes using logistic regression and will be presented as an (unadjusted and adjusted) odds ratio of outcomes in the waterbirth group compared with the birth on land group. Parameter estimates will be provided alongside 95% CI and p-value. Secondary outcomes will have non-inferiority testing as detailed above.

	Maternal	Adverse neonatal
	outcome: OASIS	composite outcome
Maternal age (years)	√	$\checkmark$
Maternal BMI	✓	
Parity	√	
Duration of labour	✓	
Gestational age at delivery (weeks)	√	$\checkmark$
Child birth weight (g)	✓	$\checkmark$
Child head circumference (cms)	√	
Maternal thyroid disease (including hypothyroidism)		$\checkmark$
Pre-labour ruptured membranes		$\checkmark$

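### The comparator is defined by the reason for leaving the pool, but that reason is not recorded before site opening, and the OASIS analysis uses births from 2015

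*Protocol*

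**What the plan says.** **Who is compared.** Section 7 compares low-risk women who gave birth in water with low-risk "women who left the water prior to birth for reasons other than clinical need (Group 2"). Other sections are wider:

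- The aim in section 5, repeated in the synopsis and section 3, asks whether "waterbirth, compared to leaving a pool prior to birth, is as safe for mothers and babies", whatever the reason for leaving.
- Section 9.6.5 states: "The primary analyses are based on a non-inferiority test of birth in water versus on land".
- Section 9.6.4 sets the inclusion rules and removes births before arrival and intentionally unattended births. It does not remove clinical exits.

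Section 4 says that both kinds of exit occur: "leaving the pool either prior to birth due to clinical concerns or maternal choice".

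**What is recorded, and when.** Section 5.4 says "Additional data items with accompanying background development required to fully answer the research aims will be added to E3 systems at study sites". The list that follows includes "Reason for leaving pool if prior to birth" and "Maternal risk factors developing during labour".

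**Which births are used.** For OASIS, section 7 says "this analysis will use a combination of retrospective and prospectively collected data, including births from 2015 to 2020". The reason given is that perineal trauma and waterbirth are already in the records. Section 9.3 likewise sends births from January 2015 to the maternal outcomes.

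**The concern.** Section 7 justifies the retrospective births by the availability of the outcome (OASIS) and the exposure (waterbirth). It is silent on the third thing needed, membership of Group 2. That depends on why the woman left the pool, which the existing record does not hold as a field.

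Elsewhere the protocol respects this limit. The neonatal primary outcome is prospective only because one component is not in older records, and section 9.6.1 says the same of placental delivery in water. Retrospective secondary neonatal outcomes are used only where risk status and pool use can be determined. The OASIS analysis carries no such condition.

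Two things are at stake. The retrospective and prospective births may be compared against different groups and then pooled. The two primary outcomes may also end up with different comparators. In a non-inferiority analysis with margins of 1.0 and 0.6 pp, a small shift in the comparator rate can decide the conclusion.

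**Working it through.** **1. The plan's own figure.** Inputs from section 9.6.1: OASIS 4.6% (nulliparous) and 1.6% (parous), margins 1.0 and 0.6 pp, one-sided 5%, 90% power, true difference zero.

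n per group = 2p(1−p)(1.645 + 1.282)² / margin²

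- Nulliparous: 7,517
- Parous: 7,491

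Both agree with the stated 7,500, so the sample-size arithmetic is not at fault.

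**2. Share of the period without the recorded reason.** January 2015 to November 2020 is 71 months. Section 7 starts prospective collection in June 2018, so January 2015 to May 2018 is 41 months: 41/71 = 0.577. This assumes even accrual. Growth in waterbirths would lower the share and staggered site opening would raise it.

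**3. Possible shift, nulliparous stratum.** The protocol gives neither the share of clinical exits (f) nor their OASIS rate, so both are assumptions. Only the retrospective part is affected.

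- Bias = 0.577 × f × excess
- SE of the difference at 7,500 per group = √(2 × 0.046 × 0.954 / 7,500) = 0.342 pp
- Chance of declaring non-inferiority when waterbirth is truly 1.0 pp worse = Φ(bias/0.342 − 1.645)
- Power at no true difference = Φ((1.0 + bias)/0.342 − 1.645)

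| f | OASIS excess in clinical exits | Bias | False non-inferiority | Power at no true difference |
|---|---|---|---|---|
| none | – | 0 | 5% | 90% |
| 20% | +1 pp | +0.12 pp | 10% | above 90% |
| 30% | +3 pp | +0.52 pp | 45% | above 90% |
| 50% | +4 pp | +1.15 pp | 96% | above 90% |
| 30% | −3 pp | −0.52 pp | below 1% | 40% |

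The last row shows the reversal: clinical exits with less OASIS, for example because many end in caesarean birth.

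A second parameterisation gives a similar picture. Suppose the whole comparator were affected, with a 25% clinical-exit share. A rate ratio of 1.5 lifts the nulliparous comparator rate from 4.6% to 5.18% (+0.575 pp) and false non-inferiority to 47%. A ratio of 0.5 lowers the rate by 0.575 pp and cuts power to 36%. In the parous stratum a ratio of 1.5 shifts the rate by 0.20 pp, a third of the 0.6 pp margin. If only retrospective births are affected, these shifts are multiplied by about 0.58.

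**4. Power if OASIS is restricted to births with a recorded reason, nulliparous.** Power = Φ(1.0/SE − 1.645), SE in pp.

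- 1,650 per year (section 9.6.1) × 2.5 years = 4,125 per group: SE 0.461 pp, power 70%
- 15,000 prospective pool births (section 9.6.6) × 25% nulliparous (section 9.6.1) = 3,750 per group: SE 0.484 pp, power 66%
- 4,125 water and an assumed 8,250 land: SE 0.399 pp, power 80%

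The planned 90% therefore leans on records that lack the field defining the comparator.

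**The case against.** **A proxy may exist.** A reader might infer that the retrospective comparator can only be everyone who left the pool. The protocol does not establish that. Section 9.2 describes E3 as a comprehensive data set, and mode of birth is an outcome that is not among the new items. Figure 1 is not shown and the SAP is not at hand, so either could hold a rule. This stands. But any proxy would still differ from the section 7 definition, and the text fixes none.

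**Direction.** A reader might also infer that the mixing favours waterbirth. That is plausible if clinical exits include many assisted births with more OASIS, but no figure in the protocol shows it, and caesarean births would pull the other way. This objection stands in full.

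**Adjustment and sensitivity analyses.** Candidate covariates for OASIS include duration of labour, birth weight and head circumference, which could absorb part of a shift. Propensity-score and instrumental-variable analyses are planned, the latter aimed at unobserved selection. The sizes above are unadjusted, so this tempers them. It does not settle who belongs in the comparator.

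**The wider wording may be the intended one.** If the comparator is simply everyone who left, the retrospective data pose no problem of identification. Section 7 then needs changing, and the inconsistency remains either way.

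**Conclusion.** The point holds as a defect in a stated rule for a primary outcome. The comparator is worded in incompatible ways. Under the restricted wording of section 7, Group 2 cannot be identified by its own definition for about 41 of 71 months of the OASIS data. Births after site opening have the reason recorded and do not share that problem, although the inconsistent wording affects them too.

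Confidence is high on the inconsistency and the missing rule, but not on direction or size. A bias of about half the nulliparous margin, with false non-inferiority near 45%, rests on an assumed 30% share, an assumed 3 pp excess, even accrual and no adjustment. With the opposite sign, the same size of bias leaves about 40% power. Either could undermine the maternal conclusion, so this should be settled before the analysis.

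**What to change.** 1. Use one comparator definition in the synopsis and in sections 3, 5, 7, 9.6.4 and 9.6.5. If clinical exits are to be excluded, section 9.6.4 should say so.
2. State in section 9.6.4 how retrospective leavers are classified, using fields present in all years. Check the rule against the recorded reason in the prospective births and report the misclassification. The rule should not select on events after leaving the pool, such as mode of birth, unless the change of estimand is acknowledged.
3. Pre-specify a prospective-only OASIS analysis using the recorded reason, reported beside the pooled 2015–2020 result.
4. Give its power in section 9.6.1 with the assumptions: about 66–70% for nulliparous women at 3,750–4,125 per group, 1:1, and higher with accrual growth or a larger land group.

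The cost is revised wording, one extra analysis, and a stated power for that analysis below the planned 90% under these assumptions. No further data items are needed.

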### 8 Site and Investigator selection

The study will include maternity units in the UK that use the EuroKing® E3 maternity information system. The sites will also have to have functioning birthing pools to be included within the study.

Before any Site can begin recruitment a Principal Investigator (PI) at each site must be identified. The following documents must be in place and copies sent to the POOL Study email account (see contact details on page 4):

- > The approval letter from the site's R&D Department
- Favourable opinion from Main Ethics committee
- A signed Study Agreement

Upon receipt of all the above documents, the Study Manager will send written confirmation to the Principal Investigator detailing that the centre is now ready to open. This letter/email must be filed in each site's Site File.

Occasionally during the study, amendments may be made to the study documentation listed above. CTR will issue the site with the latest version of the documents as soon as they become available. It

TPL/003/2 v1.0

Page **18** of **38** 

is the responsibility of the CTR to ensure that they obtain local R&D approval for the new documents.

Site initiation will be by attendance at a national POOL launch meeting / site visit/ or by teleconference if attendance of key personnel is unfeasible.

### 9 Cohort Study

### 9.1 Population

The target population is all women with an uncomplicated pregnancy, who meet NICE criteria for being at 'low risk' of complications at labour onset and who use water immersion during labour.

### 9.2 Data sets

To answer the research questions, it is planned to use two datasets, data extracted from EuroKing® maternity information systems and data held by the National Neonatal Research Database. EuroKing's Maternity Information System, "E3", forms a comprehensive clinical data set and is currently used by 35 maternity NHS Trusts and Health Boards in the UK. All 200 neonatal units in England, Wales and Scotland form the United Kingdom Neonatal Collaborative (UKNC) and contribute electronic health record data to the National Neonatal Research Database (NNRD). The NNRD is a national resource formed of the Neonatal Data-Set (an NHS Information Standard), comprising 450 clearly defined variables extracted at patient level from the commercial Electronic Health Record used by all UK neonatal units.

### 9.3 Study Procedures

To answer the research questions, demographic and clinical data relating to all births at participating sites during the period of retrospective and prospective data collection will be extracted as follows:

- 1. Maternity sites will be recruited by Cardiff University and all required permissions obtained.
- 2. Data relating to births from January 2015 onwards and captured in EuroKing® prior to site opening will be extracted and transferred to Cardiff University. This retrospective data will be identified by EuroKing® mother and baby numbers only and contribute to the maternal outcomes for the study.

- Additional data items essential to the study, but not currently in the E3 system, including a screening question to identify women with complicating factors on pool entry, will be added to the system at each participating site.
- 4. Following three months of prospective data collection, and each quarter thereafter, data relevant to the study and captured in E3 systems at each study site will be extracted by EuroKing®.
- 5. EuroKing® will allocate each mother and baby a linking identifying number, remove NHS and hospital numbers, and other identifiable variables and forward the data to Cardiff University.
- 6. On a quarterly basis, the NHS and EuroKing® numbers of all babies born at units during that period, and whose mother used a pool in labour, will be extracted and passed onto the NNRD for matching. The transfer process will be managed by EuroKing® throughout the duration of the study. E3 systems are installed locally on premises at each NHS Trust / Health Board therefore each set of data extractions must be managed on a site by site basis by EuroKing®.

To Note. Data extraction from sites on a quarterly basis is required as less frequent extractions may result in challenges for sites with less powerful servers, and ensures timely matching of maternal and neonatal data between EuroKing® and the NNRD.

### 9.4 Creation of pseudonymised dataset in Cardiff University

Each phase of data extraction syntax can be run remotely from study sites by EuroKing®. Cardiff University will receive only pseudonymised data. For EuroKing® data transferred directly to Cardiff University from study sites, we will utilise a secure method of case labelling which will involve generating a unique study number for each mother and baby recoded from their NHS number, which also facilitates a link between each mother / infant dyad. This unique study number will be generated prior to data leaving the study sites. A separate syntax, will direct the NHS number of babies born to all women who used a pool during labour, after site opening, to the NNRD on a quarterly basis. Any NNRD matched data will undergo the identical secure method of case labelling of the babies NHS numbers prior to data being transferred back to Cardiff University. Use of this method of case labelling will enable Cardiff University only to hold pseudonymised data, whilst facilitating the identification of mother / infant dyads and enable the matching of the neonatal unit admission record onto to the EuroKing® mother and baby record. See Figure 2.

TPL/003/2 v1.0

Page 20 of 38

[figure not shown]

Figure 2 Data Flow

